## **1.9 SAFETY ENDPOINTS**

Not applicable.

## **1.10 OTHER ENDPOINTS**

Not applicable.

## **1.11 COVARIATES**

Not applicable.

## **HANDLING OF MISSING VALUES**

Missing data patterns, including the amount of missing data for each variable and individual and possible reasons for missing data, will be explored. As this is a descriptive study, missing data will not be imputed. The number and percentage of patients with missing data will be reported for each variable.

## **STATISTICAL METHODOLOGY AND STATISTICAL ANALYSES**

### **1.12 STATISTICAL METHODS**

Descriptive statistics will be presented separately for the demographic, clinical, and outcome characteristics of COVID-19 patients taking Paxlovid, and for COVID-19 patients who were offered Paxlovid therapy but who refused treatment. Inferential statistics will be used to assess any differences in demographic characteristics, clinical characteristics, and disease outcomes between patients who received Paxlovid and patients who refused Paxlovid.

PFIZER CONFIDENTIAL

CT24-WI-GL03-RF03 2.0 *Non-Interventional Statistical Analysis Plan For Secondary Data Collection*  
*Study 01-Jun-2020*  
Page 13 of 22

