### Inferential statistics

Between-group differences in categorical variables will be examined using proportions tests, Chi-square tests of independence or Fisher exact tests as appropriate. Differences in continuous variables will be examined using independent t-tests.

Differences in proportions or means (as appropriate) and 95% confidence intervals between COVID-19 patients taking Paxlovid, and COVID-19 patients who were offered Paxlovid therapy but who refused treatment will be reported. Additionally, Cramer's V or Cohen's d will be reported.

Cramer's V is a measure of association that quantifies the strength and direction of the relationship between the two categorical variables being compared. Cramer's V ranges from 0 to 1, where 0 indicates no association between the variables, and 1 represents a perfect association. The magnitude of Cramer's V will be interpreted as follows:

Cramer's V	Effect Size
-------------------	--------------------

0.1	Weak
0.3	Medium
0.6	Large

Cohen's d quantifies the standardized difference between the means of the two groups, and is calculated by taking the difference between the means of the two groups and dividing it by the pooled standard deviation. The magnitude of Cohen's d will be interpreted as follows:

Cohen's d	Effect Size
------------------	--------------------

0.2	Small
0.5	Medium
0.8	Large

An a priori alpha level of 0.05 has been selected for all tests. As this work is exploratory no adjustment for multiple comparisons will be made.

PFIZER CONFIDENTIAL

CT24-WI-GL03-RF03 2.0 *Non-Interventional Statistical Analysis Plan For Secondary Data Collection*  
Study 01-Jun-2020  
Page 14 of 22

Selection of the control groups will consider the following characteristics based on the availability of data using propensity-score matched:

- age,
- sex,
- COVID vaccination status,
- high-risk status for severe COVID-19 outcomes (WHO definition),
- assessment of healthcare seeking behavior in 365 days prior to COVID infection (such as flu or streptococcus pneumoniae vaccine, has primary healthcare provider, number of primary care/hospital visits),
- socioeconomic factors (such as household income, employment status),
- geographic location of residence,
- comorbidities.

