### **7.2.3 Summary of Analyses**

Descriptive statistics will be presented for all variables. Inferential statistics will be used to examine difference in demographic, clinical, and outcome characteristics between COVID-19 patients who received Paxlovid and those who were offered, but refused, Paxlovid.

PFIZER CONFIDENTIAL

CT24-WI-GL03-RF03 2.0 *Non-Interventional Statistical Analysis Plan For Secondary Data Collection*  
*Study 01-Jun-2020*  
Page 15 of 22

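### The SAP tests outcomes between acceptors and refusers without covariates, and its one safeguard, a propensity-matching sentence, is unspecified and tied to no outcome table

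*SAP*

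**What the plan says.** The covariates section, SAP 1.11, reads in full "Not applicable". SAP 1.12 covers disease outcomes as well as baseline characteristics: "Inferential statistics will be used to assess any differences in demographic characteristics, clinical characteristics, and disease outcomes between patients who received Paxlovid" and those who refused. SAP 7.2.3 repeats this: "Inferential statistics will be used to examine difference in demographic, clinical, and outcome characteristics between COVID-19 patients who received Paxlovid" and those who refused.

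The methods are in SAP 1.13, under Inferential statistics. For categorical variables: "Between-group differences in categorical variables will be examined using proportions tests, Chi-square tests of independence or Fisher exact tests as appropriate". For continuous variables: "Differences in continuous variables will be examined using independent t-tests". Differences with 95% confidence intervals, and Cramer's V or Cohen's d, go with them. Alpha is 0.05 for all tests. The shell for Table 7 has p-value and effect-size columns for hospitalization, ICU admission, ventilation and length of stay; the shell for Table 6 has them for death. No outcome analysis includes a baseline variable.

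The same section ends with: "Selection of the control groups will consider the following characteristics based on the availability of data using propensity-score matched". The list that follows contains age, sex, vaccination status, "high-risk status for severe COVID-19 outcomes (WHO definition"), healthcare seeking over the prior 365 days including hospital visits, socioeconomic factors, residence and comorbidities.

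SAP 1.1, Study population and 1.5 describe the controls as about 1000 patients who were offered the drug and refused it, against about 3000 treated. None of these sections mentions matching. Protocol 9.1 says healthcare resource use will be compared; protocol 9.7 gives no method of adjustment.

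**The concern.** Patients who accept an offered drug may differ from those who refuse it in age, immune status, comorbidity and earlier hospital use. The documents themselves attach different hospitalization rates to the WHO risk tiers, so a difference in case mix alone produces a difference in hospitalization.

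The matching sentence is the only thing between that mix and Table 7. As written, an analyst could run plain tests on all acceptors against all refusers and still be following SAP 1.11, 1.12 and 7.2.3. Another could match first and get a different answer. Neither analysis would adjust for imbalance left over after matching. At stake is whether the reported differences in hospitalization, ICU use and death can be read as anything more than differences in who said yes.

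**Working it through.** **Step 1: what the matching sentence settles.** It names a method and a list of characteristics. It does not give the propensity model, ratio, caliper, replacement rule, balance check, treatment of missing score variables, or the tables that use the matched set. Household income and employment status are on the list but not among the variables in SAP Tables 1, 2 and 4. The independent t-tests take no account of pairing. Objectives (ii) and (iii) test differences in age, sex and comorbidities, which matching is meant to remove, so those comparisons point to an unmatched cohort.

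**Step 2: room for matching.** Matching 1:1 without replacement keeps at most min(3000, 1000) = 1000 pairs, so at least 2000/3000 = 67% of treated patients are dropped. At a 3% rate the 95% half-width is 1.96 × √[0.03 × 0.97 × (1/n₁ + 1/n₂)]: 1.2 percentage points for 1000 vs 3000, and 1.5 for 1000 vs 1000. Of the 8263 in the full analysis set, 8263 − 3000 − 1000 = 4263 belong to neither described group, and the SAP does not present them as a pool of controls.

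**Step 3: size if the comparison is unmatched.** The plan gives no figure to reproduce. Inputs from the documents:
- hospitalization rates of 6% (high risk), 3% (moderate) and 0.5% (low), stated after SAP Table 4 and in protocol 9.7;
- 3000 treated and 1000 refusers;
- alpha 0.05, taken as two-sided.

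Assumed: no drug effect, and the tier mixes below.

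Group rate = Σ (tier share × tier rate). For example, 0.20 × 0.06 + 0.70 × 0.03 + 0.10 × 0.005 = 3.35%, and 0.10 × 0.06 + 0.60 × 0.03 + 0.30 × 0.005 = 2.55%. Then SE = √(0.0335 × 0.9665/3000 + 0.0255 × 0.9745/1000) = 0.00597 and z = 0.0080/0.00597 = 1.34. The rejection probability is Φ(z − 1.96) + Φ(−z − 1.96) = 26.8%. The last column simulates the chi-square test that the SAP names.

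| Treated mix (high/mod/low, %) | Refuser mix | Rates | Ratio | Rejection, formula | Rejection, chi-square |
|---|---|---|---|---|---|
| 10/80/10 | 10/80/10 | 3.05% vs 3.05% | 1.00 | 5% | 5% |
| 20/70/10 | 10/80/10 | 3.35% vs 3.05% | 1.10 | 7.6% | 7% |
| 10/70/20 | 5/65/30 | 2.80% vs 2.40% | 1.17 | 10.8% | 9% |
| 20/70/10 | 10/60/30 | 3.35% vs 2.55% | 1.31 | 26.8% | 23% |
| 10/60/30 | 20/70/10 | 2.55% vs 3.35% | 0.76 | 24.1% | 28% |

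**Step 4: information for an adjusted model.** At an assumed 3%, 4000 × 0.03 = 120 hospitalizations are expected unmatched, and 2000 × 0.03 = 60 with 1000 pairs. Objective (iv) in the SAP uses a five-day follow-up, against 28 days in the protocol, so there may be fewer.

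**The case against.** The best defence is the matching sentence itself. A reader who sees covariates declared not applicable might infer that differences in age, risk tier and prior hospital use go straight into the resource-use result. The documents do not support that: all three are on the matching list, and matching is a recognised way to control confounding. If it were carried out and achieved balance, the differences in Step 3 would largely vanish. That stands, and it limits the point to what happens if matching is absent, partial or confined to some tables.

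Second, the work is called exploratory, SAP 1.3 and 1.4 set no hypotheses or decision rules, and protocol 9.9 limits the findings to association. A test that detects a true crude difference of 3.35% vs 2.55% is not wrong as description. That also stands: the rejection rates above are errors only if the result is read as an effect of the drug. But p-values and intervals on clinical outcomes, by treatment received, invite that reading, and protocol 9.9 does not mention confounding.

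Third, the larger figures need a 20-point gap in the low-risk share. Patients were offered the drug because of age or a listed condition, so a 30% low-risk share is doubtful. With low risk held at 10% in both groups, rejection is only about 7%. The low end of the range is therefore as plausible as the high end.

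**Conclusion.** The concern holds in a conditional form. It is certain from the text that covariates are declared not applicable, that outcome tests are unadjusted, and that the matching is unspecified, conditional on data availability and unconnected to any outcome table. It is not established that the reported outcomes will be confounded; that depends on whether matching is done and what imbalance it leaves.

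If the comparison is unmatched, tier mix alone gives crude ratios from about 0.76 to 1.31 and rejection from about 7% (small gap) to 27% (large gap), in either direction. These figures rest on assumed mixes, no drug effect and the documents' tier rates. They do not describe a matched analysis.

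**What to change.** 1. In SAP 1.11, replace the present entry with a short, non-overlapping list from the data to be extracted. For example: age in years, sex, vaccination status, immunosuppression, number of the other listed risk factors (leaving out age and immunosuppression), and any hospitalization in the baseline year.
2. In SAP 1.13, state that the baseline comparisons for objectives (ii) and (iii) use the unmatched cohort, and name the sample that feeds Table 7. If that sample is matched, give the score model, ratio, caliper, replacement rule, balance check and handling of missing score variables.
3. In Table 7, report beside the crude hospitalization result a covariate-adjusted risk difference and risk ratio. Use a logistic model with standardization and a bootstrap or robust 95% interval, respecting the pairs if matched.
4. For rare outcomes (ICU admission, IMV, death), adjust for the propensity score alone, or label the result crude and unadjusted.

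The cost is SAP wording and one model for hospitalization. No new variables are needed as long as the listed ones are available in the records, which the SAP does not guarantee. SAP Table 4 counts hospitalizations over baseline and follow-up, so the two periods must be separated. With three vaccination levels the list above takes seven parameters plus treatment, so 120/8 = 15 events per parameter unmatched but 60/8 = 7.5 with 1000 pairs, and fewer over five days. The number of terms should be set by the events observed.

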## 1.13 STATISTICAL ANALYSES

### Descriptive statistics

Categorical variables will be presented in terms of raw numbers (n) and percentages (%). Continuous variables will be presented as means and standard deviations or as medians and interquartile ranges, depending on the level of skewness and kurtosis of the data.

### Inferential statistics

Between-group differences in categorical variables will be examined using proportions tests, Chi-square tests of independence or Fisher exact tests as appropriate. Differences in continuous variables will be examined using independent t-tests.

Differences in proportions or means (as appropriate) and 95% confidence intervals between COVID-19 patients taking Paxlovid, and COVID-19 patients who were offered Paxlovid therapy but who refused treatment will be reported. Additionally, Cramer's V or Cohen's d will be reported.

Cramer's V is a measure of association that quantifies the strength and direction of the relationship between the two categorical variables being compared. Cramer's V ranges from 0 to 1, where 0 indicates no association between the variables, and 1 represents a perfect association. The magnitude of Cramer's V will be interpreted as follows:

Cramer's V	Effect Size
-------------------	--------------------

0.1	Weak
0.3	Medium
0.6	Large

Cohen's d quantifies the standardized difference between the means of the two groups, and is calculated by taking the difference between the means of the two groups and dividing it by the pooled standard deviation. The magnitude of Cohen's d will be interpreted as follows:

Cohen's d	Effect Size
------------------	--------------------

0.2	Small
0.5	Medium
0.8	Large

An a priori alpha level of 0.05 has been selected for all tests. As this work is exploratory no adjustment for multiple comparisons will be made.

PFIZER CONFIDENTIAL

CT24-WI-GL03-RF03 2.0 *Non-Interventional Statistical Analysis Plan For Secondary Data Collection*  
Study 01-Jun-2020  
Page 14 of 22

Selection of the control groups will consider the following characteristics based on the availability of data using propensity-score matched:

- age,
- sex,
- COVID vaccination status,
- high-risk status for severe COVID-19 outcomes (WHO definition),
- assessment of healthcare seeking behavior in 365 days prior to COVID infection (such as flu or streptococcus pneumoniae vaccine, has primary healthcare provider, number of primary care/hospital visits),
- socioeconomic factors (such as household income, employment status),
- geographic location of residence,
- comorbidities.

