### **Study population**

Patients will be eligible for inclusion in the study if they were diagnosed with COVID-19 between February and November 2022, were treated in an outpatient setting in the Kingdom of Bahrain, and were offered Paxlovid. Paxlovid was offered to patients in the Kingdom of Bahrain if they were at high risk of complications from COVID-19 due to age  $\geq$  50 years, BMI  $\geq$  35, or a medical history of chronic kidney disease (eGFR  $\geq$ 30 ml/min), diabetes mellitus, primary or secondary immunosuppressive disease or receiving immunosuppressive treatment, cardiovascular disease or hypertension, chronic lung diseases, sickle cell disease, neurodevelopmental disorders, or having a medical-related technological dependence. There are no exclusion criteria.

EHRs from approximately 3000 COVID-19 patients who were treated with Paxlovid, all of whom gave verbal consent for treatment that was recorded in the medical record, will be included in the study. These patients were treated between February and November 2022, and consist of approximately 53% of the total eligible patient population from the timeframe. A comparison group of patients will also be included. This group will consist of approximately 1000 patients with COVID-19 that were offered Paxlovid therapy but who refused treatment, over this same time period.

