## **ANALYSIS SETS/POPULATIONS**

### **1.5 FULL ANALYSIS SET**

The full analysis set will consist of approximately 8263 adult COVID-19 patients with pre-existing comorbidities who attended outpatient clinics in the Kingdom of Bahrain. It includes approximately 3000 patients who received Paxlovid and approximately 1000 COVID-19 patients who were offered Paxlovid therapy but who refused treatment.

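### SAP 1.13 selects controls by propensity-score matching but names only independent-sample tests and intervals; no stated variance method fits matched sets, and whether the matched sample is tested is unclear

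*SAP*

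**What the plan says.** Two statements stand in the same part of SAP 1.13, Inferential statistics.

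- **How controls are formed:** "Selection of the control groups will consider the following characteristics based on the availability of data using propensity-score matched", followed by eight characteristics. No ratio, replacement rule or caliper is given, and nothing is said about unmatched patients.
- **How groups are compared:** "Between-group differences in categorical variables will be examined using proportions tests, Chi-square tests of independence or Fisher exact tests as appropriate"; and "Differences in continuous variables will be examined using independent t-tests". Estimates are promised as "Differences in proportions or means (as appropriate) and 95% confidence intervals between COVID-19 patients taking Paxlovid" and refusers. On the error rate: "An a priori alpha level of 0.05 has been selected for all tests".

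No paired, conditional, weighted or cluster-robust method appears anywhere in the SAP. Covariates (1.11) and Analyses of Endpoints (1.13.2) are marked not applicable. Sections 1.5 and 1.7 define no matched analysis set. In the protocol, propensity-score matching appears only in the abbreviation list.

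Other SAP sections describe the comparison without matching. Section 1.5 says of the full analysis set: "It includes approximately 3000 patients who received Paxlovid and approximately 1000 COVID-19 patients who were offered Paxlovid therapy but who refused treatment". Study population gives the same two counts, and Statistical Methods (1.12) and Summary of Analyses (7.2.3) contrast received with refused.

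**The concern.** Matching makes the two groups dependent, in one of two ways.

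- Members of a matched set share a similar score. Outcomes that the score predicts are then positively correlated within the set, and an independent-sample standard error is too large.
- There are about three treated patients per refuser, the reverse of the usual surplus of controls. One-to-one matching of every treated patient needs controls to be used repeatedly. If each use is a separate row, the named tests count the same people several times and the standard error is too small.

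SAP objectives (ii) to (iv) are answered by these tests, and the results fill the p-value and effect-size columns of Tables 3, 6 and 7. The intervals are promised in the text of 1.13; the table shells have no column for them. The point concerns the variance and the test only, not the choice of matching variables or the loss of treated patients.

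**Working it through.** The documents contain no power or precision calculation, so there is no planned figure to reproduce.

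**Inputs from the SAP:** about 3000 treated and about 1000 refusers (Study population; 1.5); alpha 0.05, taken as two-sided; hospitalization rates of 6%, 3% and 0.5% by WHO risk tier (Endpoints and Covariates).

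**Assumed, because the documents give no value:** the within-set correlation rho, and the effective number of controls (ESS) under reuse.

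**Case A: no control reused.** For n one-to-one pairs in SD units, the true SE is sqrt(2(1 − rho)/n) and the independent-test SE is sqrt(2/n). Their ratio is sqrt(1 − rho). For K treated per control, the variance within a set is (1 + (K − 1)rho)/K + 1 − 2rho = ((K + 1)/K)(1 − rho), so the same ratio holds for sets of three treated to one refuser. The interval is too wide by 1/sqrt(1 − rho) − 1, and the actual type I error is 2Φ(−1.96/sqrt(1 − rho)).

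| rho | interval too wide by | actual type I error |
|---|---|---|
| 0 | 0% | 5.0% |
| 0.05 | 2.6% | 4.4% |
| 0.1 | 5.4% | 3.9% |
| 0.2 | 11.8% | 2.8% |
| 0.3 | 19.5% | 1.9% |
| 0.5 | 41.4% | 0.6% |

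Power shows the practical cost. With 1000 pairs and an assumed difference of 0.125 SD, the independent test has 80.4% against 81.8% for the paired test at rho 0.05, 81.1% against 83.8% at 0.1, and 84.1% against 91.6% at 0.3.

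*Rare binary outcome matched only on risk tier.* Here rho = var(p)/(p̄(1 − p̄)) over the three tier rates. The tier mix is not given, so two are assumed.

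- 10% high, 80% moderate, 10% low: p̄ = 0.0305, var = 0.000152, rho = 0.000152/0.02957 = 0.005. Intervals are 0.3% too wide.
- Equal thirds: p̄ = 0.0317, var = 0.000506, rho = 0.000506/0.03066 = 0.016. Intervals are 0.8% too wide and type I error is 4.8%.

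**Case B: all 3000 treated matched one-to-one, controls reused, each reuse an independent row.** The true variance is 1/3000 + 1/ESS, ignoring within-set correlation. The test assumes 2/3000. Type I error is 2Φ(−1.96/ratio), where ratio is true SE over assumed SE.

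| ESS | true SE / assumed SE | interval too narrow by | actual type I error |
|---|---|---|---|
| 1000 (each used three times) | sqrt(2) = 1.41 | 29% | 16.6% |
| 750 | sqrt(2.5) = 1.58 | 37% | 21.5% |
| 500 | sqrt(3.5) = 1.87 | 47% | 29.5% |

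If instead each control is counted once (assumed variance 1/3000 + 1/1000), the ratio is 1.0 with even reuse, so nothing is understated. At ESS 500 it is 1.32 and type I error is 13.8%.

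**Simulation checks, no treatment effect.** In 4000 replicates, 3000 treated and 1000 controls were matched to the nearest neighbour on the score. Rejection rates at rho of about 0.05, 0.2 and 0.5 were:

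- One-to-one pairs, independent t-test: 4.0%, 2.7% and 0.5%.
- The same pairs, paired t-test: 4.4%, 4.9% and 4.5%.
- Reused controls as rows (ESS about 482), independent t-test: 29%, 24% and 14%. The rate falls as rho rises because the two kinds of dependence offset each other.

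A separate simulation of 10,000 runs at a 3% event rate gave 16.2% with even reuse and 21.9% with random reuse. Clustering on the control brought these to 5.3% and 5.6%.

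**The case against.** **The tested sample may not be matched at all.** Sections 1.5, 1.12 and 7.2.3 and Study population can be read as a plain comparison of about 3000 treated with about 1000 refusers. On that reading independent-sample tests are formally valid, and the weakness is lack of adjustment, which is a different point. This stands. It also leaves the matching sentence in 1.13 with no role, so the SAP still has to say which sample is tested.

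**Reuse is nowhere stated.** The 17% figure needs three choices that the SAP does not make: every treated patient kept, controls reused, and each reuse entered as its own row. The control group is described as patients: "This group will consist of approximately 1000 patients with COVID-19 that were offered Paxlovid therapy but who refused treatment". This stands in full. A reader might infer that hospitalization, ICU and death comparisons will show false differences at three to four times the nominal rate; the documents do not support that as a prediction.

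**Without reuse the error is on the safe side.** This also stands. A propensity score pairs patients on one number, so two patients with the same score can differ in age, comorbidity and vaccination. Nothing in the documents supports a correlation as high as 0.3 to 0.5. At 0.05 to 0.1 the power loss in the example is 1 to 3 points.

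**The work is exploratory, without hypotheses or decision rules.** That limits the consequence and is the SAP's reason for not adjusting for multiplicity. It does not justify reporting p-values and 95% intervals without a variance method that fits the sample.

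**Conclusion.** The gap is real: the SAP matches controls and then names only methods for independent samples, with nothing elsewhere to fill it. Better methods exist and cost little.

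The size is conditional. Without reuse, the p-values and intervals are conservative: intervals are about 3%, 5% and 20% too wide at assumed correlations of 0.05, 0.1 and 0.3, and under 1% too wide for hospitalization matched only on risk tier under the two mixes shown. With all treated patients matched, controls reused and each reuse counted as a row, the nominal 5% test rejects about 17% of the time with even reuse, and more with uneven reuse (29.5% by formula at 500 effective controls).

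A reader might infer that the planned p-values and intervals are simply wrong. The documents do not support that. They do not fix the matching design, and on the unmatched reading the named tests are valid. What they do support is that the SAP commits to no variance method suited to the matching it describes.

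**What to change.** In SAP 1.13:

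1. Keep the independent-sample tests for the unmatched description of received against refused (Table 3).
2. Define the matched analysis set, the matching ratio and the replacement rule, and say that the matched comparison of clinical characteristics and outcomes fills Tables 6 and 7.
3. For that comparison, report the difference in proportions or means with its 95% interval and p-value from a regression on treatment, with robust standard errors clustered on the matched set, and also on the control's patient ID if any control is reused.
4. Allow McNemar and paired t-tests only for complete one-to-one pairs. Missing data are not imputed, and some Table 7 rows apply only to a subset, such as patients with readmissions, so many pairs may be incomplete.

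**Cost:** a short addition to the SAP and no new data. The matched-set identifier must be kept in the analysis file, and intervals will widen if controls are reused.

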Non-invasive Ventilation Usage	Non-invasive ventilation usage during COVID-related hospitalizations in the baseline and follow-up periods (excluding within 24 hours of Paxlovid initiation)
High-flow Nasal Cannula Usage	High-flow nasal cannula usage during COVID-related hospitalizations in the baseline and follow-up periods (excluding within 24 hours of Paxlovid initiation)
Hospital Discharge Status	Patient discharge status for COVID-related hospitalizations during the baseline and follow-up periods (excluding within 24 hours of Paxlovid initiation)

PFIZER CONFIDENTIAL

CT24-WI-GL03-RF03 2.0 *Non-Interventional Statistical Analysis Plan For Secondary Data Collection*  
*Study 01-Jun-2020*  
 Page 11 of 22

Time from COVID-19 Test to Paxlovid Treatment	Time from the earliest COVID-19 test in the baseline period to the earliest date of Paxlovid prescription written date AND dispense date.
COVID-19 Lab Tests with Positive Result	COVID-19 lab test with a positive result during the baseline and follow-up periods.
COVID-19 Lab Test with Variant Type	When available, COVID-19 variant of concern (VOC) during the baseline period.
Treatment drugs being receiving at the index date	-Use Positive test as the INDEX Date and record use of any medicine listed in the potential DDI/Contraindications section of the EUA/:Label
Monoclonal Antibody Usage	Monoclonal antibody usage during the baseline and follow-up periods. Monoclonal antibody usage will include tocilizumab and bamlanivimab/etesevimab. (Yes/No)
Antiviral Usage	Antiviral therapy usage during the baseline and follow-up periods. Antiviral therapy usage will include remdesivir, nirmatrelvir/ritonavir (paxlovid) and molnupravir. (Yes/No)
Steroid therapy	Steroid therapy during admission (Yes/No)

PFIZER CONFIDENTIAL

CT24-WI-GL03-RF03 2.0 *Non-Interventional Statistical Analysis Plan For Secondary Data Collection*  
*Study 01-Jun-2020*  
 Page 12 of 22

WHO guidelines on COVID-19 therapeutics include the following groups

- **High risk:** people who are immunosuppressed; estimated hospitalization rate of 6%.
- **Moderate risk:** >65 years of age, conditions like obesity, diabetes and/or chronic conditions including chronic obstructive pulmonary disease, kidney or liver disease, cancer, with disabilities, and with comorbidities of chronic disease; estimated hospitalization rate of 3%.
- **Low risk:** those who are not in the high or moderate risk categories; low risk of hospitalization (0.5%) – most people are low risk.

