**Table 7: Descriptive statistics for outcome variables**

Outcome Variables	Group		P-value	Effect size
	Paxlovid	Control		
Hospitalizations, % (n)				
Number of hospitalizations per patient, mean (SD)				
Number of hospitalizations per patient among patients with readmissions, % (n)				
Time to first outpatient encounter, mean (SD)				
ICU Admission, % (n)				
Hospital Length of Stay, mean (SD)				
ICU/Non-ICU LOS, mean (SD)				
IMV/No IMV LOS, mean (SD)				
Treatment				
IMV Usage, % (n)				
Supplemental Oxygen Usage, % (n)				
Non-invasive Ventilation Usage, % (n)				
High-flow Nasal Cannula Usage, % (n)				
Hospital Discharge Status				
Went home, % (n)				
Transfer to skilled nursing facility, % (n)				

PFIZER CONFIDENTIAL

CT24-WI-GL03-RF03 2.0 *Non-Interventional Statistical Analysis Plan For Secondary Data Collection Study* 01-Jun-2020

Page 20 of 22

Transfer to other healthcare facility, % (n)				
Transfer to other long-term care facility, % (n)				
Transfer to hospice, % (n)				
Death, % (n)				
Medication Usage, % (n)				
Antibiotic, % (n)				
Antiviral (incl. Paxlovid, COVID-19 monoclonal antibodies), % (n)				
Antithrombotic, % (n)				
Anti-inflammatory (incl. steroids), % (n)				

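### Cramer's V is wrongly described as showing direction, its fixed labels do not suit rare binary outcomes, and the outcome shells have no column for the promised differences with 95% CIs

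*SAP*

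**What the plan says.** SAP section 1.13, under Inferential statistics, plans differences in proportions or means with 95% confidence intervals, and in addition Cramer's V or Cohen's d. It says that V "quantifies the strength and direction of the relationship between the two categorical variables being compared". The next sentence gives V a range from 0 to 1. Then "The magnitude of Cramer's V will be interpreted as follows": 0.1 is weak, 0.3 medium and 0.6 large. These are single values, not bands, and they apply to every categorical variable.

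The shells (SAP Tables 3, 6 and 7) have four columns: Paxlovid, Control, P-value and Effect size. The first row of the Table 7 outcome shell reads "Hospitalizations, % (n)". Death and inpatient death stand at the end of Table 6. No shell has a column for a difference or its interval.

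SAP section 1.5 says the full analysis set includes "approximately 3000 patients who received Paxlovid and approximately 1000 COVID-19 patients who were offered Paxlovid therapy but who refused treatment". After SAP Table 4, the WHO risk groups are listed with hospitalization rates: "people who are immunosuppressed; estimated hospitalization rate of 6" percent for high risk, "with comorbidities of chronic disease; estimated hospitalization rate of 3" percent for moderate risk, and 0.5% for low risk.

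**The concern.** Three things do not fit together.

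- **Direction.** A statistic bounded by 0 and 1 cannot show which group did better.
- **Labels.** In a 2×2 table the size of V depends on how common the event is and how unequal the groups are, as well as on the effect. When events are rare, V stays far below 1 even if one group has none. Fixed labels then describe the rarity of the event as much as the difference between groups.
- **Display.** The text promises differences with intervals, but the shells give them no place. Tables programmed from the shells would carry a P-value and an effect size and could omit the one measure that gives sign, size and precision.

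At stake is how the hospitalization, ICU, ventilation, oxygen and death comparisons are read. A large relative reduction could be described as weak beside a very small P-value.

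**Working it through.** The documents state no value of V and no power calculation, so there is no figure to reproduce.

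**Inputs.** Group sizes of about 3000 and 1000 (SAP 1.5). Control rates of 0.5%, 3% and 6% (WHO groups after SAP Table 4). Labels 0.1, 0.3 and 0.6 (SAP 1.13). The SAP mentions propensity-score matching without a ratio, so 1:1 (1000 vs 1000) is shown as an assumption.

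**Formula.** For a 2×2 table, V = √(χ²/N) = |p₁ − p₂| · √(q(1−q)) / √(p̄(1−p̄)), where q is the treated share and p̄ the pooled rate.

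**Worked case.** Take 0/3000 treated against 30/1000 control events. Then q = 0.75, p̄ = 30/4000 = 0.0075, and V = 0.03 × √0.1875 / √(0.0075 × 0.9925) = 0.01299 / 0.08628 = 0.151. The uncorrected Pearson chi-square on the same counts is 90.68, and √(90.68/4000) = 0.151, which agrees.

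**Most extreme benefit (zero treated events), and the 88% reduction that the SAP introduction cites for hospitalization or death:**

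| Control rate | Zero treated, 3000 vs 1000 | Zero treated, 1000 vs 1000 | 88% reduction, 3000 vs 1000 |
|---|---|---|---|
| 0.5% | 0.061 | 0.050 | 0.046 |
| 3% | 0.151 | 0.123 | 0.114 |
| 6% | 0.214 | 0.176 | 0.162 |

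Every entry is below 0.3. At 3000 vs 1000 with zero treated events, the Fisher P-value is 0.001 at 0.5% and below 10⁻¹⁸ at 3%.

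**Control rate needed to reach a label.** With zero treated events, V² = qp / (1 − (1−q)p), so p = V² / (q + V²(1−q)).

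- Medium (0.3): 0.09 / (0.75 + 0.0225) = 11.7% at 3:1, and 0.09 / (0.5 + 0.045) = 16.5% at 1:1.
- Large (0.6): 0.36 / (0.75 + 0.09) = 42.9% at 3:1, and 0.36 / (0.5 + 0.18) = 52.9% at 1:1.

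**Which label applies.** The SAP gives points, not bands.

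- Read as lower cut-offs, the zero-event cases at 3% and 6% are weak, and the 0.5% case has no label.
- Read as nearest value, the boundary between weak and medium is 0.2. The 6% case at 3:1 (0.214) becomes medium, and all the other zero-event cases are weak.

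**Direction.** With 1000 per group, 0% vs 6% and 6% vs 0% both give V = 0.176.

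**What the promised difference would show** (3000 vs 1000, zero treated events, Newcombe 95% CI):

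- control 0.5%: −0.5 points (−1.2 to −0.2)
- control 3%: −3.0 points (−4.3 to −2.1)
- control 6%: −6.0 points (−7.6 to −4.7)

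**The case against.** The best defence is that V is secondary. The SAP commits to differences with 95% CIs and adds V or d to them. It calls the work exploratory, and it lists hypotheses and decision rules as not applicable, so no conclusion hangs on a label. This stands as a limit on the consequences. It does not repair the wrong description of V or the missing column.

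Several stronger readings are tempting, and the documents do not support them:

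- *That no label can ever be reached.* The 0.1 value is reached at 3% and 6%. Only 0.3 and 0.6 are out of reach, and only at control rates like these.
- *That harm and benefit would look alike in the tables.* V alone cannot tell them apart, but the shells print each group's percentage, so a reader can see which is higher.
- *That a weak label will certainly be published.* The shell column is headed only Effect size, and no shell has a place for a verbal label. The label also depends on whether the listed values are cut-offs or nearest points.
- *That the calculation covers every hospitalization row.* The 0.5%, 3% and 6% figures are WHO group estimates. SAP Table 4 counts all-cause as well as COVID-related admissions, over baseline and follow-up, and protocol section 9.3 sets baseline at one year. All-cause admissions over that span could be more common, and the documents give no rate.
- *That the whole Effect size column should go.* Table 6 is mostly symptoms, comorbidities, vaccination status and risk factors. Vaccination status (three levels) and discharge status (six levels) have no single risk difference, and the mean (SD) rows of Table 7 use Cohen's d.

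**Conclusion.** Wrong as written, and worth correcting before the tables are programmed. The statement about direction is an error by the SAP's own range for V. The labels are unsuitable for rare binary outcomes: at about 3000 vs 1000 and control rates of 0.5%, 3% and 6%, even complete elimination gives V = 0.06, 0.15 and 0.21, and assumed 1:1 matching gives 0.05, 0.12 and 0.18. None reaches the medium value of 0.3. Whether a given case is called weak depends on a reading that the SAP leaves open, and at 6% and 3:1 the nearest-value reading gives medium.

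The conclusion is confined to COVID-related follow-up events at about these rates. It no longer holds once the control risk passes about 12% (3:1) or 17% (1:1). The text and the shells also disagree, because the promised differences and intervals have no column. The harm is limited, since the group percentages are shown and no decision rule uses V.

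**What to change.** - In SAP 1.13, delete the words that credit V with direction.
- State that the verbal V labels are not applied to binary outcome rows.
- Add a column for the risk difference (Paxlovid minus control) with 95% CI, optionally with a risk ratio, to the binary outcome rows of Table 7 and to the death and inpatient death rows of Table 6.
- In the same column, give the mean difference with 95% CI for the mean (SD) rows.
- Keep V for baseline and multi-level categorical rows such as vaccination status and discharge status, and keep Cohen's d for continuous rows.

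The cost is a few SAP sentences and one shell column. The differences and intervals are already promised, so only the optional risk ratio is new, and no further data are needed.
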